The parameters of interest are δ_k , which are a (log) odds-ratio for the prevalence outcome and a mean absolute difference in score for the three individual-level outcomes. We will take both intention to treat (ITT) and per protocol approaches for the individual level outcomes. For the ITT analysis, the variable D_{jt} is an indicator equal to one if cluster j is in the intervention state at time t and zero otherwise. Thus, δ represents our estimated treatment effect. For the per protocol analysis, D_{ijt} will be a patient-level variable equal to one if the clinic was in the intervention state and the patient completed the treatment as defined above, and zero otherwise. As we describe below, we will use a randomisation test method to derive exact inferential statistics (p-values and confidence intervals) for the parameters of interest.

Outcomes 2-4 described above are only recorded for those who screen positive for depression at their scheduled visit. Thus, the data do not all cover the full patient population: data for outcomes 2 to 4 are a subset of those for outcome 1. Based on this, we anticipate the data to be normally distributed. However, we will test this assumption by examining QQ plots and conducting KS (Kolmogorov Smirnov) and SW (Shapiro Wilk) tests. In the event the normality assumption is violated, we will consider an alternative specification, such as a two-part semi-continuous model.

Statistical Inference

All models will be estimated separately using restricted maximum likelihood, using the R package lme4. We will report point estimates, confidence intervals, and p-values but not make any claims of "statistical significance", given recent strong arguments against doing so [2].

P-values will be based on the null hypotheses $H_0: \delta_k = 0$ versus the two-sided alternatives $H_1: \delta_k \neq 0$ in each of the models defined above. Given that there are multiple primary outcomes, we will adjust reported p-values for multiple testing using a cluster-based stepdown method, which provides an efficient means of controlling the family-wise error rate [18]. The full methodology is described elsewhere, but we describe it here briefly.

Let there be P hypotheses to be tested H_1, \dots, H_P with associated test statistics T_p . We let the ordered test statistics be:

$$T_{[1]} \geq T_{[2]} \geq \dots \geq T_{[P]}$$

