corresponding to hypotheses $H_{[1]}, \dots, H_{[P]}$. The family of hypotheses being tested is $K \subset \{1, \dots, P\}$. We first describe a stepdown procedure for the decision to accept/reject given a value for the type I error rate α , as this provides a clear way of deriving the associated p-value that we will report.[4] The stepdown method works by firstly testing if the joint null hypothesis is true by comparing the largest test statistic to the critical value $c_K \left(1 - \frac{\alpha}{2}\right)$. If it is smaller than this critical value, we accept all null hypotheses; otherwise, we reject $H_{[1]}$ and test the remaining hypotheses as a new family in the same way. More specifically, the algorithm is:

1. Let $K_1 = \{1, \dots, P\}$. If $T_{[1]} \leq c_{K_1} \left(1 - \frac{\alpha}{2}\right)$, then accept all hypotheses and stop, otherwise reject $H_{[1]}$ and continue.
2. Let K_2 be the indices of hypotheses not previously rejected. If $T_{[2]} \leq c_{K_2} \left(1 - \frac{\alpha}{2}\right)$ then accept all remaining hypotheses, otherwise reject $H_{[2]}$ and continue.

The critical values here are the $1 - \frac{\alpha}{2}$ quantiles of the distribution of the largest test statistic for the relevant family of hypotheses. Exact distributions may not exist; however, we can derive them using a pseudo-permutation testing approach by enumerating a large number of permutations (e.g. 100,000 permutations) following a randomisation test approach based on the cluster randomisation.

At each stage of the stepdown algorithm, we are testing the largest test statistic, that is: $T_K = \max_{q \in K} T_q$. If the associated hypothesis is rejected, we create a new family of hypotheses that excludes the rejected hypothesis. If we re-randomise the clusters, then for each permutation $m = 1, \dots, M$, we can re-calculate the desired test statistic, $T_K^{(m)}$, to create our reference distribution. The p-value is then:

$$p_{[k]} = \frac{1}{M} \sum_{m=1}^M I(T_K^{(m)} \geq T_K)$$

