That is to say that the reference distribution for the largest test statistic is the largest test statistic from the permutations of the remaining hypotheses, and so on (see also [4–6]). The test statistics we will use are the studentised, generalised residuals from each of the models, which are optimal for randomisation tests for cluster-based analyses and exponential family models,[7] and also ensure each of the individual tests in the family of tests has the same power since the test statistics will be of equivalent scale.[5]

The procedure above can be used to derive a set of confidence intervals for the parameters of interest that has nominal “family-wise coverage”, as described by Watson et al [TBA]. We will estimate 95% confidence intervals for the set of treatment effect parameters following this method.

Missing Data

We foresee the main risk in terms of missing data to be patients whose depression status may cause them to miss appointments and hence have fewer observations during the trial. This mechanism would generate data missing *not at random* (MNAR). Alternative mechanisms include data entry error and (conditionally) random patient no-shows to appointments (e.g. older patients are less likely to attend), both of which would be missing at random (MAR) or missing completely at random (MCAR). It is not possible to distinguish between MNAR and

MAR empirically.[8] Thus, to provide information about the possible mechanism of missingness in the data, CHWs tasked with following-up with patients will be asked to identify a main reason for the missed appointments in an anonymous reporting form. For example, reasons may include “mental health/emotional issues” or alternative such as “was not able to attend due to other commitments”. A qualitative judgement will be made on the basis of these data by the trial team as to what the most likely/common cause of missingness is likely to be. We also note that the CHW follow-up process should also limit the extent of missing data in this study.

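### The stepdown's 1 − α/2 cut-off and its undoubled p-value differ by a factor of two, and no definition of T makes both right

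*SAP*

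**What the plan says.** The SAP, Statistical Inference, tests a null effect for each of the four primary outcomes "versus the two-sided alternatives". At each step it takes the largest statistic in the remaining family, T_K, and compares it with a re-randomisation distribution of that maximum. The critical values are the 1 − α/2 "quantiles of the distribution of the largest test statistic for the relevant family of hypotheses", where α is described as the type I error rate of the decision. If T_K does not exceed the cut-off, the instruction from the second step on is to "then accept all remaining hypotheses, otherwise reject" the hypothesis in question and continue. The SAP gives this rule because "this provides a clear way of deriving the associated p-value that we will report". The p-value is then printed as the proportion of permuted maxima at or above T_K, with no factor of two.

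The intervals rest on the same material: "The procedure above can be used to derive a set of confidence intervals for the parameters of interest that has nominal" family-wise coverage, by a method whose reference is still to be added. The SAP continues: "We will estimate 95% confidence intervals for the set of treatment effect parameters following this method". The Statistical model section promises that "we will use a randomisation test method to derive exact inferential statistics (p-values and confidence intervals) for the parameters of interest". The account is openly partial: "The full methodology is described elsewhere, but we describe it here briefly".

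**The concern.** One statistic and one reference distribution are used at two different tail levels. A cut-off at 1 − α/2 suits one tail of a signed statistic. An undoubled upper-tail share is a two-sided p-value only if the statistic is a magnitude. The SAP does not say which kind of statistic T is, and neither choice reconciles the two lines.

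This matters because the trial will make no claims of statistical significance, so the adjusted p-values and family-wise intervals are its whole inferential output for the primary outcomes. A programmer who follows the text could produce intervals that disagree with the p-values, or p-values at half their two-sided size.

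A smaller point is that the algorithm stops at the first acceptance and does not say what adjusted p-value is reported for the outcomes still in the family. On its own that would only call for clarification.

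**Working it through.** **Inputs.** α = 0.05 (Protocol, Sample Size). Four hypotheses, two-sided alternatives, the cut-off and the p-value formula are from the SAP, Analysis of Primary Outcomes and Statistical Inference. The correlation r between the outcomes' statistics is not given, so 0, 0.3 and 0.6 are assumed.

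**Step 1: the identity.** Let p be the share of permuted maxima at or above T_K. Then T_K > c_K(1 − α/2) holds exactly when p < α/2, apart from ties. At α = 0.05 the rule rejects only when the printed p is below 0.025. This holds for any T.

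**Step 2: does the rule have error rate α?** Take four independent standard normal statistics. The cut-off at level q is z((1 + q^(1/4))/2) for the maximum of |T|, and z(q^(1/4)) for the maximum of signed T.

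| Reading of T | Printed cut-off (q = 0.975) | Family-wise error | Family-wise error of printed p ≤ 0.05 |
|---|---|---|---|
| Absolute | 2.731 | 0.0250 | 0.0500 (cut-off 2.491) |
| Signed, upper tail only (literal) | 2.494 | 0.0250, one-sided | 0.0500, one-sided |
| Signed, applied to both tails | 2.494 | 0.0495 | 0.098 |

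No row has both lines at 5% for a two-sided test. The literal signed reading also looks only upward, whereas the SAP expects prevalence and severity to fall. In an illustrative simulation with three negative effects and one null, p ≤ 0.05 occurred in 90% of trials with |T| and 1.4% with signed T.

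**Step 3: size with |T|** (1,000,000 multivariate-normal draws).

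| Outcomes left | r | Printed cut-off | Cut-off at 1 − α | Ratio |
|---|---|---|---|---|
| 4 | 0 | 2.730 | 2.490 | 1.096 |
| 4 | 0.3 | 2.718 | 2.473 | 1.099 |
| 4 | 0.6 | 2.674 | 2.414 | 1.108 |
| 1 | any | 2.24 | 1.96 | 1.14 |

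The ratio is the relative interval width if intervals are built from the printed cut-off. First-step family-wise coverage is then 1 − 0.025 = 97.5%.

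**Step 4: a worked case, r = 0.** Suppose the largest statistic is 2.60, so Φ(2.60) = 0.99534.
- With |T|, p = 1 − (2 × 0.99534 − 1)^4 = 0.037. Yet 2.60 < 2.73, so the rule accepts, and an interval using the printed cut-off includes zero.
- With signed T, p = 1 − 0.99534^4 = 0.0185, half the two-sided value.

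**Step 5: how often p and interval would conflict.** This is the chance that one given outcome's |T| lies between the two first-step cut-offs, over r = 0 to 0.6:
- expected statistic 0: 0.6–0.8%
- expected statistic 1.96: 7.7–8.8%
- expected statistic 2.49: 9.5–10.3%
- expected statistic 4: 3.6–3.7%

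**Step 6: check by re-randomisation.** The simulation used 14 clinics in arms of 3, 3, 3, 3 and 2, six periods, 30 patients per clinic-period, ICC 0.05, CAC 0.80 and IAC 0.80, with 1,999 permutations and 40,000 null trials per r. Family-wise error with |T| was 4.9–5.2% at 1 − α and 2.4–2.6% at the printed cut-off. Intervals were 10–11% wider. The simulation simplified the trial to a closed cohort, with linear models for all four outcomes and no excluded allocations.

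**The case against.** The strongest reply is that little depends on the cut-off. Ranking hypotheses by their largest statistic under two-sided alternatives makes sense only if T is a magnitude, and then the printed p-value, which is what will be reported, is right. The accept/reject rule is only expository, and no decision will be announced from it. The SAP does not say that the intervals use the cut-off: inverting the printed p-value at 0.05 with |T| would give intervals with nominal 95% family-wise coverage that agree with the p-values. Any error in this case is conservative. The signed reading would miss the expected benefits, so it is unlikely to be intended. The full method is said to be described elsewhere.

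Much of this stands. |T| is the natural reading, and the p-values are sound under it. The interval problem arises only if the intervals are built from the cut-off line, and family-wise error is not inflated in that case. The fuller source cannot be checked here, so the criticism is limited to the SAP text.

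The reply does not remove the contradiction. The 1 − α/2 level appears four times, so it is not a stray symbol. The SAP says that the p-value follows from a rule it does not match. T is left undefined in sign, and the interval construction points back to a procedure containing both levels, with its own reference still to be supplied.

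**Conclusion.** The concern holds: the cut-off and the p-value are inconsistent by an exact factor of two, whatever the data. With |T|, the cut-off is wrong (2.5% instead of 5%). With signed T, the p-value is one-sided and the lower tail is never tested, so at least one line is wrong and, read literally, both are deficient.

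The practical size is small. On the |T| reading the reported p-values are unaffected. The exposure is intervals about 10% too wide at the first step, with a conflict between p and interval for a given outcome in at most about 10% of trials. These sizes rest on approximately normal statistics, the assumed correlations, and intervals built from the printed cut-off. If α/2 were kept for a signed T, the exposure would be p-values at half their two-sided size. This is a minor error in the text, to be corrected before the analysis code is final.

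**What to change.** In the SAP, Statistical Inference:

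1. Define T_k as the absolute (or squared) studentised statistic.
2. Replace 1 − α/2 by 1 − α throughout the critical values.
3. Keep the printed p-value formula and add p_[k] = max(p_[k−1], p_[k]), so that all four outcomes receive an adjusted p-value consistent with the stopping rule.
4. State that the 95% family-wise intervals invert this same rule, and complete the outstanding reference.

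An almost equivalent alternative is to keep 1 − α/2 with signed T, write out the lower-tail step and double the p-value. Its first-step cut-offs are 2.50, 2.48 and 2.41 at r = 0, 0.3 and 0.6, against 2.49, 2.47 and 2.41 for the main proposal.

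The cost is a few lines of text and code, with no new data and no design change. If T was always meant to be absolute, only its definition, the quantile, one sentence on monotone p-values and one on the intervals need to be written.

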In most of Malawi, including in Neno District, the usual care procedure for addressing depression is for patients who self-present with significant symptoms such as psychosis, suicidal ideation or attempt or potential harm to others receive a referral either to a mental health clinical officer or nurse within the district (in Neno District there are three), or else to a mental health specialist at a regional hospital. Due to the limited supply of mental health clinicians in Neno District, those with comorbid conditions such as schizophrenia or more complex mood disorders such as bipolar disorder are prioritized for immediate intervention. Of those who presently receive treatment for overt mood disorders, treatment typically comprises pharmacotherapy—including fluoxetine or amitriptyline for depressive symptoms with individual counseling if time and staff is available. There is currently no system-wide model in IC3 or primary services for screening for depression. However, Neno District has begun

screening and treatment for peripartum depression at one antenatal clinic—a system separate from the IC3 system which is the focus of this work. The inclusion of depression screening and psychoeducation, features of the control arm of this study, represent modest enhancements of the existing system from which the full IC3 model will be introduced.

With regard to IC3, services are condition-specific. To provide an example: HIV/AIDS is the most common chronic care condition treated at IC3, constituting approximately 70% of enrollees. Patients receiving antiretroviral therapy attend clinic every three to six months for evaluation (e.g. screening, adherence, viral load) and are provided with a necessary supply of antiretroviral medications until their scheduled return date. Patients with non-suppression, missed appointments or poor adherence are evaluated on a monthly basis. Non-communicable disease (NCD) patients attend clinic every 3 months with 1-month appointments with poor disease control or missed appointments. They are screened for comorbid disease (e.g. HIV, tuberculosis [TB], other NCDs) and provided with necessary supply of medications to their scheduled return date.

Treatment: IC3D

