If the data are considered to be (mostly) MAR or MCAR then they do not present a risk of bias for our analyses; however, the uncertainty may be under-estimated. If this is the case, and there exists a substantial proportion (> 10% missing) of missing data, then a secondary analysis will be conducted using multiple imputation methods. If the data are determined to be (mostly) MNAR then a secondary analysis that attempts to jointly model the outcome, covariates, and missingness mechanism will be conducted: in particular, a random coefficient pattern mixture model approach will be used, which has previously been shown to provide reliable inferences for longitudinal data with MNAR data, particularly in the case where drop out may be due to a decline in functioning over time.[9]

Secondary Outcomes

The analysis plan will also include several secondary analyses, in which we focus on the relationships between the intervention and physical health outcomes—such as HIV, diabetes, and hypertension—as well as theoretical moderators, including fidelity to protocols among providers, levels of social support received by participants, and perceived internalized stigma among patients. For physical health outcomes, the same model specification will be used as described above. For evaluation of the effect of the intervention on potential moderators, the relationships will predominately be examined through interaction models, in which we will include an interaction term of the treatment effect with variables measuring fidelity, social support and stigma in the models. While examining the relationships among these variables, the research team may also consider mediator pathways for social support and stigma, whereby the intervention leads to changes in social support and stigma, which (in turn) lead to reductions in depression symptoms.

Addendum: Added 18 November, 2021

Implementation outcomes

We propose to add a more detailed and explicit assessment of the implementation of the intervention as a secondary analysis. The primary aim of the trial remains to estimate the effectiveness of the intervention from an intention-to-treat perspective. However, given the novelty of our approach, understanding the context for implementation and the barriers to successful adoption and integration of mental health interventions is an important secondary aim. The trial is thus a “hybrid effectiveness-implementation trial” according to the schema outlined by Wolfenden et al. (2021) [10]

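### The SAP's one analysis of its stated main missing-data risk runs only if the trial team judges missingness to be mostly MNAR

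*SAP*

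**What the plan says.** All of the rule is in the SAP, Missing Data. It opens with the risk the authors fear most: "We foresee the main risk in terms of missing data to be patients whose depression status may cause them to miss appointments". It classes that mechanism as MNAR, and lists data entry error and conditionally random no-shows, for example among older patients, as MAR or missing completely at random (MCAR). It then concedes: "It is not possible to distinguish between MNAR and" MAR from the data.

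To fill that gap, community health workers who follow up absent patients "will be asked to identify a main reason for the missed appointments in an anonymous reporting form". Next, "A qualitative judgement will be made on the basis of these data by the trial team" about the commonest cause. The answer selects one of two branches:

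- **Mostly MAR or MCAR.** On bias, the SAP says of the missing data: "then they do not present a risk of bias for our analyses". Multiple imputation is added as a secondary analysis only if "there exists a substantial proportion (> 10% missing) of missing data".
- **Mostly MNAR.** A random-coefficient pattern-mixture model is fitted as a secondary analysis.

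The SAP gives no threshold for *mostly*, no time at which the judgement is made, and no MNAR analysis that runs by default.

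**The concern.** Collecting reasons for absence is sensible. The weakness is using them as a switch. A single label for the whole trial hides a mixture of causes, and one main reason per missed appointment already simplifies each case. If depression explains a large minority of absences, the label is MAR/MCAR, the no-bias sentence applies, and no reader sees how far the results depend on the mechanism the SAP itself puts first.

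No blinding is described for the team that makes the judgement, and no date is set for it, so the choice of branch could be made with results in view.

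Missingness can plausibly differ between control and intervention periods. Better retention in IC3 care is one of the objectives in the Protocol's Introduction, so the intervention is meant to change who attends. Informative absence that differs by state biases the treatment contrast as well as the level.

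**Working it through.** The point concerns a decision rule, and the plan offers no computed figure for it to reproduce. Two document figures enter: 15% loss to follow-up (Protocol, Sample Size) and the 10% imputation threshold (SAP, Missing Data). Using the 15% as the share of data missing is an assumption.

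**Step 1: what the rule does.** Read *mostly* as more than 50% (assumption). Informatively missing share = share missing × share of that due to depression.

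| Missing | Due to depression | Label | Analysis run | Informatively missing |
|---|---|---|---|---|
| 10% | 49% | MAR/MCAR | none | 0.10 × 0.49 = 4.9% |
| 15% | 49% | MAR/MCAR | multiple imputation only | 0.15 × 0.49 = 7.35% |
| 15% | 51% | MNAR | pattern-mixture model | 0.15 × 0.51 = 7.65% |
| 25% | 49% | MAR/MCAR | multiple imputation only | 0.25 × 0.49 = 12.25% |

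The second and third rows are almost the same situation, yet only one gets an MNAR analysis. The 49% is chosen to sit just under the cut, so 7.35% is close to the most that can go unexamined at 15% missing.

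**Step 2: possible bias in PHQ-9 severity.** Let m be the share missing in a state and g the amount by which absent patients score above attenders. The attenders' mean is too low by m × g. The contrast, intervention minus control, is therefore shifted by (m_control − m_intervention) × g. Assume 15% missing under control, 5% to 10% under IC3D, and g of 2 to 4 points:

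- Smallest: (0.15 − 0.10) × 2 = 0.1 points.
- Largest: (0.15 − 0.05) × 4 = 0.4 points.

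A beneficial effect is negative on this scale and the shift is positive, so the estimated benefit shrinks. With the two missing shares exchanged, the shift is −0.1 to −0.4 points and the benefit is inflated. On the 0-27 scale this is 0.1/27 = 0.4% to 0.4/27 = 1.5% of the range. The formula uses raw means; the patient random effects in the planned model may absorb part of the shift.

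**Step 3: outcome 1 (prevalence).** The SAP, Analysis of Primary Outcomes, holds only the number screened and the number with depression per cluster and step. The model for these totals has cluster-level covariates and random effects for cluster and cluster-time. The SAP's own MAR example is that older patients attend less, but a patient's age cannot enter that model. For outcome 1 the no-bias sentence therefore holds under MCAR, or where the cluster covariates explain the missingness, and not for MAR in general.

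For scale, take 10% true prevalence (the Protocol's Sample Size figure), suppose 15% of depressed patients are absent, and suppose everyone else attends (assumptions). Observed prevalence is 0.10 × 0.85 / (0.10 × 0.85 + 0.90) = 0.085/0.985 = 8.6%, and the odds are multiplied by 0.85. This reaches the treatment odds ratio only so far as absence differs between states.

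**The case against.** The strongest reply is that the plan is coherent and better than many. It admits that the mechanism cannot be settled from the data and for that reason seeks outside information. It names a specific MNAR model in advance, and follow-up by community health workers should limit the loss. Both missing-data analyses are secondary, so the primary estimates are the same in either branch. If absence depends on scores already observed, the mixed model handles part of it. The illustrative bias is small on the PHQ-9 scale and, in the likelier direction, conservative. All of this stands. It limits the size of the point but does not justify making the MNAR analysis conditional on a label.

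A reader might infer more than the documents support:

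- *The SAP contradicts itself.* It does not. Seeking reasons for absence follows from its statement that the data cannot decide.
- *The judging team is unblinded.* No text says so. The Protocol has the principal investigators execute the randomization and describes no blinding of team or analysts; that is as far as it goes.
- *The forms cannot be linked to clinic or period.* The SAP calls them anonymous and does not say whether clinic or step is recorded.
- *The 10% threshold counts quarters in which nobody was due.* The Protocol does say: "Patients receiving antiretroviral therapy attend clinic every three to six months for evaluation". But the SAP speaks of missed appointments and scheduled visits, and a quarter without an appointment is neither.
- *The no-bias sentence is simply false for outcome 1.* It holds there under MCAR. The Protocol, Analysis of Intervention Effects, also expects to link each patient who takes a PHQ-9 screening; the restriction to totals comes from the SAP.

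Bounding outcome 1 by active minus screened patients is also tempting. It would count patients who were not due as missing, and the bounds would be wide: with 10% positive among those screened and 15% unscreened (assumptions), 0.85 × 0.10 = 8.5% to 8.5% + 15% = 23.5%.

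**Conclusion.** The point holds as a gap in the sensitivity analysis. As written, the rule can leave the SAP's stated main risk unexamined: about 7% of data informatively missing with no MNAR analysis, given 15% missing, 49% of it due to depression, and *mostly* read as over half. At 10% missing or less under the same label, no missing-data analysis runs at all. The illustrative effect on PHQ-9 severity is 0.1 to 0.4 points in either direction, resting on assumed missing shares and score gaps. What is at stake is whether readers can see how sensitive the primary estimates are, not the estimates themselves. The no-bias sentence is also too broad: it needs the variables that drive missingness to be in the model, and for outcome 1 patient-level variables cannot be. This should be changed before analysis, but it does not threaten the design.

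**What to change.** In the SAP, Missing Data:

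1. Run the random-coefficient pattern-mixture analysis for outcomes 2-4 whatever the forms show. Keep multiple imputation alongside it when more than 10% of due visits are missing, and state that the percentage refers to due visits.
2. Report the reason forms descriptively, by clinic and step if these are recorded, and drop their role in choosing the analysis.
3. Replace the no-bias sentence with a conditional one, for example: *If data are MAR given the covariates and observed outcomes in the model, missingness is not expected to bias the analyses of outcomes 2-4. For outcome 1 this applies only under MCAR or where the cluster-level covariates explain the missingness.*

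The cost is one secondary analysis that the SAP already names, and a few sentences of text. The design and the primary analysis do not change.
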